## 11.2.3 Additional analysis

Not Applicable

#### 11.2.4 The level of significance

A p-value less than 0.05 was considered significant and was denoted by alternative hypothesis and p-value more than 0.05 was denoted by null hypothesis.

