## 3.2 Study endpoints:

#### 3.2.1 Primary endpoint:

Fugl-Meyer Assessment for Upper Extremities (FMA-UE)

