# 11. Statistical Considerations

## **11.1 Sample size Determination**

Based on the recommendations by Lewis and Sauro (2009), a minimum of 12 participants per group is considered appropriate for usability testing. In this study, participants will be categorized into four subgroups based on muscle tone classification (MAS < 1 or MAS  $\geq$  1) and treatment allocation (experimental or control group), resulting in a minimum required sample size of 48 (12 participants per subgroup). To account for an anticipated dropout rate of approximately 25%, an additional 12 participants will be recruited, leading to a total target enrollment of 60 stroke patients. In addition, 10 trained healthy participants—including caregivers or family members—will be included for usability assessments and device operation training. The total number of evaluable subjects for the study will therefore be 70.

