## **11.2 Planned Statistical methods of analysis**

Continuous variables will be presented as means and standard deviations, while categorical variables will be reported as frequencies and percentages. Independent sample t-tests will be used to compare continuous variables between groups, and Pearson's chi-square test will be used for comparisons of categorical variables. One-way analysis of variance (ANOVA) will be applied to assess differences among the multiple subgroups. All statistical analyses will be conducted using SPSS (Statistical Package for the Social Sciences). A p-value of less than 0.05 will be considered indicative of statistical significance.

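### Section 11.2.4 assigns p above 0.05 to the null hypothesis, and no confidence interval for the between-arm FMA-UE difference is planned to show what a non-significant result leaves open

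*Combined protocol and SAP*

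**What the plan says.** Section 11.2.4 pairs p below 0.05 with the alternative hypothesis, then adds that a "p-value more than 0.05 was denoted by null hypothesis". There is no third outcome.

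Section 11.2 gives only the significant half of the rule: "A p-value of less than 0.05 will be considered indicative of statistical significance". The Statistical methods item of the Synopsis does the same. Section 11.2.4 is therefore the only place that says what a non-significant p-value stands for.

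The planned between-group comparison is in Section 11.2: "Independent sample t-tests will be used to compare continuous variables between groups". That section also plans group means with SDs, chi-square tests and one-way ANOVA across subgroups. No confidence interval, equivalence margin or target difference appears there or in the Synopsis. Section 11.2.1 lists the endpoints without a method, and Section 11.2.3 (additional analysis) is marked not applicable.

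The primary endpoint is FMA-UE (Section 3.2.1). The sample size in Section 11.1 has another basis: "a minimum of 12 participants per group is considered appropriate for usability testing". Four subgroups of 12 give 48 evaluable patients, and 12 more are added for dropout, "leading to a total target enrollment of 60 stroke patients". Under Section 11.4, incomplete cases are dropped.

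**The concern.** A p-value above 0.05 means that the data did not reject the null hypothesis. It does not mean that they support it. For a two-arm t-test the null is equal means, so following Section 11.2.4 literally turns an uninformative result into apparent support for equal means. This is an error at any sample size. It has more consequence when the trial was not sized for the endpoint being tested, because a real benefit can then easily yield p above 0.05.

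A confidence interval is the usual safeguard, since it shows which effects remain plausible, and none is planned. Section 11.5 also asks that any departure from the statistical design be explained in the final report. Taken literally, an analyst who interpreted a non-significant result correctly would be departing from the written rule.

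**Working it through.** **Inputs from the documents.** Significance level 0.05 (Sections 11.2 and 11.2.4); independent-samples t-test (11.2); 48 evaluable and 60 enrolled (11.1); complete cases only (11.4).

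**Assumptions, because the documents are silent.** Two-sided test; 1:1 allocation, implied by equal subgroups of 12 but not stated; true benefit between 0.3 and 0.8 SD of the analysed variable, with 0.5 SD taken as moderate. Section 3.2.1 does not say whether the variable is the post-treatment score or the change.

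**The plan's own figure.** 4 × 12 = 48 and 48 × 1.25 = 60, which matches the stated enrolment. That gives 24 evaluable per arm as planned, or 30 per arm with no dropout. If 25% of the 60 were lost, 60 × 0.75 = 45 would remain.

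**Chance of p above 0.05 despite a true benefit.** With n per arm and a true difference of d SD, the t statistic has 2n − 2 degrees of freedom and noncentrality d × √(n/2). For d = 0.5 the noncentrality is 0.5 × √12 = 1.73 at n = 24 and 0.5 × √15 = 1.94 at n = 30. Exact noncentral-t power, and its complement:

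| True benefit | Power, 24 / 30 per arm | Chance of p above 0.05, 24 / 30 per arm |
|---|---|---|
| 0.3 SD | 17.4% / 20.8% | 83% / 79% |
| 0.5 SD | 39.6% / 47.8% | 60% / 52% |
| 0.8 SD | 77.4% / 86.1% | 23% / 14% |

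Power reaches 50% at 0.58 SD with 24 per arm and at 0.52 SD with 30 per arm. With 45 evaluable in total, power at 0.5 SD is 37.5%. Within one MAS stratum (12 per arm) it is 22%.

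**What a confidence interval would show.** Half-width in SD units = t(0.975; 2n − 2) × √(2/n):

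- n = 24: 2.013 × 0.2887 = 0.58 SD
- n = 30: 2.002 × 0.2582 = 0.52 SD

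An observed difference of 0.2 SD at 24 per arm gives 0.2 ± 0.58, or −0.38 to 0.78 SD. This is non-significant and does not exclude a 0.5 SD benefit. More generally, to exclude 0.5 SD the observed difference would have to be below 0.5 − 0.58 = −0.08 SD at 24 per arm, or 0.5 − 0.52 = −0.02 SD at 30 per arm. Under these assumptions, no non-significant result with a point estimate at or above zero rules out a 0.5 SD benefit.

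**Sensitivity of the 0.5 SD row.**

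- One-sided test: power 52.5% / 60.6%.
- Baseline-adjusted analysis, correlation r = 0.6, d replaced by d/√(1 − r²): 56.3% / 66.3%.
- Change scores, r = 0.7, 0.5 SD referring to raw scores, d replaced by d/√(2(1 − r)): 59.1% / 69.1%.
- The 60 retrospective patients pooled as controls: about 57% (24 against 84) and 65% (30 against 90).

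The plan specifies none of these four.

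**The case against.** The strongest reply is that Section 11.2.4 is a clumsy textbook label for the two outcomes of a test, reject or do not reject, and that Section 11.2 and the Synopsis state the significance threshold conventionally. Several parts of this reply stand.

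- A reader might infer that the trial will report non-significance as no difference, or as equality of the device and control training. The documents do not say so. They assign the result to the null hypothesis and stop there. The hypothesis-type line in the Synopsis does not help, because its tick marks are not legible in the text available.
- Section 11.2.4 is not the plan's only decision rule. It is one of three statements on significance, though the only one that covers p above 0.05.
- The planned group means and SDs would let a reader derive the mean difference and its interval. What is missing is a commitment to report the interval and draw the conclusion from it.
- The miss rates in the table reflect a sample size not based on FMA-UE. Rewording Section 11.2.4 does not change them.

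The label reading does not remove the fault. The sentence stands under its own heading in the statistical section, and nothing elsewhere says that non-significance is inconclusive. If failure to reject is what the sponsor means, the plan should say that.

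**Conclusion.** The point holds as a fault in the stated rule. Section 11.2.4 assigns a non-significant result to the null hypothesis, and the plan includes no interval that would show such a result to be uninformative. This part depends on no assumption about effect size.

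The size of the consequence does. Under two-sided testing and 1:1 allocation, the chance of p above 0.05 despite a real benefit runs from about 83% / 79% at 0.3 SD to 23% / 14% at 0.8 SD (24 / 30 evaluable per arm). The interval half-width is about 0.58 / 0.52 SD.

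A reader might go further and infer that a moderate benefit would be missed more often than not. The documents do not support that as a general statement, because they fix neither effect size nor sidedness. It is true at 0.5 SD under the assumptions above. It fails for effects above about 0.58 SD (24 per arm) or 0.52 SD (30 per arm), and at 0.5 SD it fails with a one-sided test. What can be said is that a non-significant FMA-UE result can be compatible with a moderate benefit and should not be read as evidence for the null.

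**What to change.** Replace the sentence in Section 11.2.4 with:

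> The between-arm FMA-UE difference will be reported with a two-sided 95% CI. p<0.05 indicates a difference; p>=0.05 means the null hypothesis is not rejected and will not be reported as no difference or equivalence; the conclusion will rest on the range of effects in the CI.

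This also covers p exactly equal to 0.05, which the current sentence leaves unassigned.

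For secondary endpoints compared between arms, likewise do not read p of 0.05 or more as support for the null, and give an interval where a two-arm difference is estimated. This does not extend to test-retest reliability, which Section 4.1 assesses in the experimental group only. The chi-square and multi-group ANOVA comparisons do not yield a single two-arm difference, so only the interpretive part applies to them.

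The cost is one replaced sentence, plus a short note for the secondary endpoints. For FMA-UE the interval is part of standard t-test output. No extra patients, visits or data are needed. The change leaves power as it is; the absence of a sample size based on FMA-UE is a separate matter that it does not address.

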## **11.3 Analysis Population**

The analysis population of this study is the patient aged 18-70 years with the onset of stroke attack within 12 months, Brunnstrom stage of upper limb >1 and Modified Ashworth Scale of upper limb < 3. All the subjects should be able to understand and cooperate with the instructions from the therapists or caregivers.

#### 11.4 Procedure for accounting for missing, unused and spurious data

The approach to the missing data is to simply omit those cases with the missing data and analyze the remaining data.

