#### 1. **Concomitant Treatments** : Not applicable

**1.** Concomitant Therapy :

**2.** Prohibited Therapy :

1. 2.	Main study Hypothesis : Equality Superiority Non-inferiority
2.	Equivalence Other
2.	
3.	Estimated Sample Size : The planned enrollment for this trial includes 60 stroke patients, with an overall evaluable sample size of 70 individuals. This estimation is based on the recommendation by Lewis and Sauro (2009), who suggest that a minimum of 12 participants is appropriate for usability assessments. In the present study, participants will be categorized into four subgroups based on MAS scores (either <1 or ≥1) and intervention type (experimental or control). To ensure that each subgroup has at least 12 participants, a minimum of 48 participants is required (12 per subgroup). An additional 25% (12 participants) will be recruited to account for potential dropout, bringing the total number of stroke patients to be enrolled to 60. Our center has the capacity to recruit and evaluate all 70 participants. In addition to prospective participants, retrospective data from 60 stroke patients will be included for analysis. Furthermore, a total of 10 individuals—including trained therapists and healthy subjects (such as caregivers or family members who have received prior instruction)— will be included to assess usability and support the study's broader evaluation framework. Efficacy assessment group : Intent-to-treat (ITT) Per-Protocol (PP) Interim analysis : Ves No
5.	Statistical methods :
	Continuous variables will be presented as means with standard deviations, while categorical variables will be expressed as proportions. Independent t-tests will be used to compare continuous variables between groups, and Pearson's chi-square test will be applied for categorical data. One-way analysis of variance (ANOVA) will be employed to assess differences across multiple groups. All statistical analyses will be conducted using the Statistical Package for the Social Sciences (SPSS). A p-value of less than 0.05 will be considered statistically significant.
6.	Handling of Missing Data :
	Only cases with complete datasets will be included in the analysis. Incomplete records will be excluded from statistical evaluation to maintain data integrity.

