## Flow Chart :

#### **4.2 Number of Patients**

Number of Patients The planned enrollment for this trial includes 60 stroke patients, with an overall evaluable sample size of 70 individuals. This estimation is based on the recommendation by Lewis and Sauro (2009), who suggest that a minimum of 12 participants is appropriate for usability assessments. In the present study, participants will be categorized into four subgroups based on MAS scores (either <1 or ≥1) and intervention type (experimental or control). To ensure that each subgroup has at least 12 participants, a minimum of 48 participants is required (12 per subgroup). An additional 25% (12 participants) will be recruited to account for potential dropout, bringing the total number of stroke patients to be enrolled to 60. Our center has the capacity to recruit and evaluate all 70 participants. In addition to prospective participants, retrospective data from 60 stroke patients will be included for analysis. Furthermore, a total of 10 individuals—including trained therapists and healthy subjects (such as caregivers or family members who have received prior instruction)—will be included to assess usability and support the study's broader evaluation framework.

framework.

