## 5.3 Withdrawal criteria

Participants will be withdrawn from the study if they (1) become lost to follow-up, (2) develop new central nervous system lesions, or (3) experience decompensated systemic diseases that may compromise safety or study participation.

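### Patients without a 3-week FMA-UE are dropped from the primary comparison, 20–25% loss is planned for, and nothing checks whether that loss relates to outcome equally in both arms

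*Combined protocol and SAP*

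**What the plan says.** - **Missing data.** Section 11.4 will "simply omit those cases with the missing data and analyze the remaining data". The synopsis is broader: "Only cases with complete datasets will be included in the analysis". Read literally, that also removes a patient who has an FMA-UE value but lacks a questionnaire.
- **Expected loss.** Section 11.1: "To account for an anticipated dropout rate of approximately 25%, an additional 12 participants will be recruited". Section 4.2: "An additional 25% (12 participants) will be recruited to account for potential dropout".
- **Outcome.** FMA-UE is the primary endpoint (section 3.2.1). The schedule in section 4.3 shows one assessment before and one after treatment.
- **Test.** Section 11.2 compares continuous variables by independent t-test. It states no baseline adjustment, and does not say whether the FMA-UE comparison uses the 3-week score or the change.
- **Blinding.** The synopsis marks the trial as open; the evaluator-blind box is not ticked.
- **Reasons for withdrawal.** Section 5.3 lists loss to follow-up, new central nervous system lesions, and patients who "experience decompensated systemic diseases that may compromise safety or study participation".
- **Other analyses.** Section 11.2.3, on additional analysis, reads "Not Applicable". No imputation, sensitivity analysis or assumption about why data go missing appears elsewhere.

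**The concern.** With a single post-treatment visit, a patient who leaves before it contributes nothing to the primary comparison. A fifth to a quarter of patients may leave, so who leaves can matter as much as how many.

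Some of the reasons in section 5.3 are plausibly tied to arm recovery. Because the arms are unmasked, patients may also leave for different reasons in each. If poorly recovering patients leave the device arm more often than the control arm, the completers' difference favours the device even when it has no effect. The reverse pattern would hide a real benefit. A reader of the final report could not tell which of these, if any, had happened.

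**Working it through.** **The plan's own loss figure**

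- Four subgroups × 12 = 48 (section 11.1).
- 48 × 1.25 = 60 reproduces the enrolment target.
- 12/60 = 20% of those enrolled, so 48 complete.
- If 25% of the 60 are lost, 60 × 0.75 = 45 complete. Keeping 48 at a true 25% loss would need 48/0.75 = 64.

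The planned loss is therefore 20% by the arithmetic and 25% as worded.

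**Condition for no bias**

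Let p be the share lost in an arm, and d the completers' mean minus the mean the lost patients would have had, in SD units. The full-arm mean is the completers' mean − p × d, so

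bias in the arm difference = p_device × d_device − p_control × d_control.

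This is zero when both d are zero, and also whenever the two products are equal.

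**Hand check** (assumed 30 per arm, 12 of 60 lost)

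- 6 v 6 lost, lost patients 0.5 SD worse in both arms: 0.2 × 0.5 − 0.2 × 0.5 = 0.
- 8 v 4 lost, 0.5 SD worse in both arms: (8/30) × 0.5 − (4/30) × 0.5 = 0.067 SD.
- 6 v 6 lost, 1 SD worse in the device arm only: 0.2 × 1 − 0 = 0.20 SD. The standard error is √(1/24 + 1/24) = 0.289, which gives a false-positive rate of 10.7% by normal approximation.

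**Simulation**

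Assumptions: no true effect, standard normal outcome, 30 per arm, two-sided 5% t-test on completers. Dropout is driven by a latent normal variable with correlation r to poor outcome. For each arm p × d = r × φ(z_p)/(1 − p), where z_p is the normal quantile at p and φ the normal density. With r = 0.5:

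- p = 10%: 0.5 × 0.175/0.90 = 0.097
- p = 15%: 0.5 × 0.233/0.85 = 0.137
- p = 20%: 0.5 × 0.280/0.80 = 0.175
- p = 25%: 0.5 × 0.318/0.75 = 0.212
- p = 30%: 0.5 × 0.348/0.70 = 0.248

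The bias column is the difference between arms; the last column comes from the simulated trials.

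| Loss, device v control | r, device v control | Bias (SD) | False positives |
|---|---|---|---|
| 20% v 20% | 0 v 0 | 0 | about 5% |
| 20% v 20% | 0.5 v 0.5 | 0 | about 5% |
| 25% v 25% | 0.5 v 0.5 | 0 | about 5% |
| 25% v 15% | 0.5 v 0.5 | 0.212 − 0.137 = 0.075 | about 6% |
| 30% v 10% | 0.5 v 0.5 | 0.248 − 0.097 = 0.151 | about 8% |
| 20% v 20% | 0.5 v 0 | 0.175 | about 9% |
| 25% v 25% | 0.5 v 0 | 0.212 | about 11% |

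The documents give no allocation ratio, no SD for FMA-UE and no link between dropout and outcome. The 30-per-arm split and every r are assumptions.

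**The case against.** **Dropout may be balanced.** New brain lesions and decompensated disease can strike either arm, and nothing in the documents ties them to the device. Equal loss with an equal link to outcome gives no bias. This stands, and it rules out two stronger readings a reader might reach for. One is that omission is valid only if loss is unrelated to recovery within each arm; the bias formula shows that equal products also suffice. The other is that a false-positive rate near 10% should be expected; that figure is the adverse end of a range that starts at 5%.

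**The skin risk in section 2.4 proves little.** A reader might infer from it that the device arm will lose its worst performers. Section 2.4 plans bandaging to prevent skin damage, section 5.3 does not list skin lesions as a withdrawal reason, and nothing links them to poor motor recovery. The inference is unsupported.

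**The plan does look at unused data.** Section 11.5 has investigators examine and record possible causes for data that are not used. That sentence follows one about ineligible patients, so its reach is uncertain. It does not test the effect of loss on the FMA-UE result.

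**Imputation from baseline adds little.** This is largely right when loss depends on recovery itself, and baseline adjustment captures most of the gain. An imputation model with many overlapping motor measures would also be fragile with about 22–24 completers per arm. The model should be small, and the shift in imputed values is what addresses the concern.

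**This is a small usability study.** Its size does rest on a usability rule, with no power basis for FMA-UE. FMA-UE is nonetheless the named primary endpoint of a randomised comparison judged at p < 0.05. The objection lowers the priority of the point but does not remove it.

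**Conclusion.** The concern holds in this form: the primary comparison rests on loss being unrelated to FMA-UE outcome, or equally related in both arms, and the plan neither states nor checks this while allowing for 20–25% loss. Under the assumptions above, bias ranges from 0 SD (about 5% false positives) with equal loss and link, through about 0.08 SD (about 6%) at 25% v 15% loss with r = 0.5 in both arms, to about 0.2 SD (9–11%) when only device-arm dropout is linked to poor outcome.

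The documents do not show that dropout will be informative or that it will favour the device. The synopsis wording on complete datasets is a firmer textual problem, since it could discard valid primary-endpoint values. The ITT and per-protocol boxes cannot be read in the text available. Under either set, the omission rule removes patients without a 3-week FMA-UE. This is a cheap improvement; the gap does not invalidate the trial.

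**What to change.** 1. In section 11.4 and the synopsis, keep the observed-data comparison, but include every patient with an FMA-UE value, not only those with complete datasets. Adjust it for baseline FMA-UE.
2. In section 11.2.3, replace "Not Applicable" with one sensitivity analysis on all randomised patients. Impute missing 3-week FMA-UE by arm from baseline FMA-UE and MAS stratum. Then shift the imputed device-arm values down in pre-stated FMA-UE point steps, and report the shift at which the conclusion changes. Say what an imputed value represents for patients withdrawn under section 5.3.
3. Report the number of patients with missing FMA-UE, and the reasons, by arm.
4. State the tipping shift next to the primary result, so readers can judge whether it is plausible. Do not use a pass-or-fail rule based on an undefined size of shift.

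Cost: plan wording and a little extra analysis on data already collected, with no added visits or patients. The downside is a somewhat wider interval and possibly a less favourable conclusion.

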## 11.5 Procedures for reporting any deviation(s) from the original statistical plan

The collected data will not be used in the statistical analysis if the patients do not meet the inclusion criteria. For unused data, the trial investigators will analyze the possible factors which cause this specific condition and record them in the case report form. Any deviation from the original statistical design must have a reasonable explanation and be reported in the final report.

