# 1. Synopsis

Protocol Title : Usability Analysis of a Novel Bilateral Upper Limb Rehabilitation Device in Post-Stroke Hemiplegia
Study Objectives :
Post-stroke patients commonly experience upper limb impairment, with approximately 85% affected during the acute phase and 40% continuing to experience dysfunction in the chronic phase. Functional upper limb use is essential for daily living and social participation. However, current rehabilitation often requires external assistance or costly robotic devices, which limits accessibility. This study proposes a novel, non-powered mechanical bilateral upper limb rehabilitation system that is easy to don and operate, reduces assistance needs, and allows patients to independently perform rehabilitation exercises. The device aims to improve treatment
accessibility and efficiency while promoting upper limb recovery. The study consists of three
phases: Prototype adjustment; Device fitting and training assessment; Usability and satisfaction evaluation.
Investigational product(s) :
A non-powered, mechanically structured bilateral rehabilitation device designed to facilitate independent upper limb training and enhance rehabilitation accessibility.
Development Phase : I III III IIV Other Not applicable
Study Design :

 
1. ■ Experimental Group : Bilateral upper limb training with the novel device + conventional occupational therapy
 
■ Control Group : □ Placebo
 
□ Study Drug (Name \ Dose \ Usage)
 
■ Other : Upper limb functional training + conventional occupational
 

therapy

 
2. Blinding : ■ Open □ Evaluator-blind □ Single-blind(patient) □ Double-blind(patient+PI)
 
□ Double Dummy □ Other
 
3. Randomization: ■ Yes □ No
 

$4 \blacksquare \text{Parallel design} \square \text{Crossover design} \square \text{Other} \square \text{Not applicable}$
4. Tratalier design Crossover design Conter Not applicable

 
6. Study Period: 1 years (2023/08/01-2024/07/31)
 

6. Dose adjustment : $\Box$ Mandatory $\Box$ Selectively $\Box$ No $\blacksquare$ Not applicable
7. Study location : Single Multi-center Global

 
Endpoints (Outcome measure) :
 
Primary endpoint:
 
Fugl-Meyer Assessment for Upper Extremities (FMA-UE)
 
Secondary endpoint:
 
Brunnstrom stage
 

- Spasticity: Modified Ashworth Scale (MAS)
- Usability: System Usability Scale (SUS)
- Test-retest reliability of repeated training sessions

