For the experimental group, patients are instructed on how to use the device, and a therapist provides assistance during operation. After the initial session, patients repeat the same training one week later to assess test-retest reliability. Training includes two components: (1) single-joint exercises targeting either the shoulder or elbow, with 20 repetitions per joint for 5 sets, each set separated by a 30-second rest; and (2) dual-joint exercises involving functional movement along rectangular and triangular paths, also conducted in 5 sets of 20 repetitions with similar rest intervals.

Control group training involves conventional functional tasks targeting the affected limb, such as box-pushing (standing or seated), alternating push-pull activities, and use of a hand-cycle. Both groups train for 30 minutes per day, five days a week, for a total of 15 sessions over three weeks. All participants continue their routine rehabilitation treatments throughout the study. At the conclusion of the three-week intervention, the rehabilitation physician reassesses Brunnstrom stage, FMA-UE, and MAS to evaluate functional changes in the affected upper limb.

To assess usability and user satisfaction, both patients and therapists complete the System Usability Scale (SUS) and a satisfaction questionnaire following the training period. The SUS consists of 10 items rated on a five-point Likert scale ranging from "strongly disagree" to "strongly agree." Odd-numbered items are positively worded, while even-numbered items are negatively worded. Scoring involves subtracting 1 from positive item scores and subtracting the original score from 5 for negative items; the total is then multiplied by 2.5 to yield a final SUS score out of 100.

The satisfaction questionnaire assesses five domains—overall satisfaction, comfort, ease of donning the device, perceived improvement in ROM, and rehabilitative assistance—using a

five-point Likert-type scale ranging from 1 (very poor) to 5 (very good).

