# 5. Study Population

#### 5.1 Inclusion Criteria

- Stroke onset  $\leq 12$  months
- Age 18–70 years
- Stable physiological and neurological status for  $\geq$ 72 hours
- Able to follow at least two-step commands
- Written informed consent obtained
- Unilateral upper limb hemiplegia
- Brunnstrom stage > I (proximal UE)
- MAS < 3 (affected UE)

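### Sections 11.3 and 11.5 let randomised patients be dropped from the FMA-UE comparison with the arm known, so the primary analysis may not include everyone randomised

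*Combined protocol and SAP*

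**What the plan says.** The synopsis marks the trial as randomised ("Randomization: ■ Yes □ No") and open ("Blinding : ■ Open □ Evaluator-blind"). FMA-UE is the primary endpoint. Section 4.1 says that after the three weeks "the rehabilitation physician reassesses Brunnstrom stage, FMA-UE, and MAS to evaluate functional changes in the affected upper limb", and it describes no masking of that physician.

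Four rules bear on who is analysed:

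- **Section 11.5:** "The collected data will not be used in the statistical analysis if the patients do not meet the inclusion criteria". It adds that reasons for unused data go in the case report form and that statistical deviations are explained in the final report.
- **Section 11.3:** the analysis population is described by age, time since stroke, Brunnstrom stage and MAS, followed by "All the subjects should be able to understand and cooperate with the instructions from the therapists or caregivers". It gives no time point and no test.
- **Section 5.3:** "Participants will be withdrawn from the study if they" meet one of three conditions: loss to follow-up, a new CNS lesion, or decompensated systemic illness.
- **Section 11.4:** the missing-data rule is to "simply omit those cases with the missing data and analyze the remaining data". The synopsis likewise keeps complete cases only.

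The synopsis field for the efficacy set prints both ITT and PP, but the mark is not legible in the text available. No legible sentence says that all randomised patients are analysed in their allocated arm. Section 11.2.3 plans no additional analysis.

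**The concern.** A randomised comparison is protected against selection only while the patients analysed are those randomised, or while any exclusion is independent of arm and outcome. Excluding on a baseline fact, judged blind to arm and outcome, does little harm. Here the rule has no time limit and no blinding, and the design is open. An eligibility question about a randomised patient could be raised, or left alone, by someone who knows the arm and perhaps the result.

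The cooperation condition adds a second opening. It is wider than the nearest entry criterion, "Able to follow at least two-step commands", and sits in the definition of the analysis population. Cooperation with a therapist can be observed during training, and training differs between the arms (guided device trajectories against box-pushing, push-pull tasks and a hand-cycle).

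At stake is whether a difference in FMA-UE can be attributed to the allocated treatment.

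**Working it through.** **1. The plan's own figure.** Sections 4.2 and 11.1: 4 subgroups × 12 = 48; 25% of 48 = 12; 48 + 12 = 60. This reproduces. The plan thus allows for 12 of 60 patients (12/60 = 20%) being lost. That allowance is for dropout, not for eligibility exclusions, and there is no power calculation for FMA-UE to reproduce.

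**2. When each rule can act.** Section 4.3 schedules the eligibility check at recruitment and at pre-treatment assessment, both before allocation. Baseline FMA-UE, Brunnstrom stage and MAS are also collected at pre-treatment. Section 4.2 adds retrospective data from 60 patients. The collected data in 11.5 may therefore belong to:

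- patients who fail screening, who are not yet randomised;
- retrospective records, which are never randomised in this trial;
- randomised patients found ineligible later.

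Nothing in 11.5 excludes the third group, and only that group affects the randomised comparison.

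**3. Illustrative shift.** Assumed: 30 per arm (the documents do not state 1:1 allocation), outcome SD = 1, and removals in the device arm only.

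If a fraction f of an arm has a mean 1 SD below the remainder, whose mean is m, the full-arm mean is (1 − f)m + f(m − 1) = m − f. Removing that fraction raises the arm mean by f.

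- 3 of 30: f = 0.10 SD
- 2 of 30: f = 0.067 SD
- Standard error of the difference: √(1/30 + 1/30) = √(2/30) = 0.258 SD
- Ratio for 3 of 30: 0.10/0.258 = 0.39 standard errors

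**4. Effect on the t-test.** Simulation with no true effect, 30 per arm, two-sided 0.05 (sidedness is not stated in the plan) and 40,000 runs per case. Removal is random in the control arm. In the device arm it falls on the lowest values of a score with correlation ρ to the outcome.

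| Removed per arm | ρ | Bias (SD) | Type I error |
|---|---|---|---|
| 3 | 0 | 0.00 | 4.9% |
| 3 | 0.3 | 0.05 | 5.5% |
| 3 | 0.5 | 0.09 | 6.4% |
| 3 | 1.0 | 0.19 | 12.3% |
| 6 | 0 | 0.00 | 5.0% |
| 6 | 0.3 | 0.10 | 6.5% |
| 6 | 0.5 | 0.17 | 9.4% |
| 6 | 1.0 | 0.34 | 26.4% |

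Removal unrelated to outcome gives no bias. The rows with 6 per arm use up the whole allowance of 12, so they describe outcome-related loss by any route and not 11.3 or 11.5 exclusions alone. Both ρ and the split between arms are assumed.

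**The case against.** The case on the other side has real force, and several stronger readings should be set aside.

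- **That 11.5 can act only on randomised patients.** A reader might infer this because eligibility is checked before allocation. The documents do not support it: the rule can also cover screen failures and the retrospective records. What stands is that it makes no exception for randomised patients.
- **That poor cooperators are removed.** Section 11.3 speaks of an ability, next to restated entry criteria, and may mean no more than the two-step-command criterion. Section 5.3 does not list non-cooperation. Removal for conduct during training is an inference; the defect is the missing time point.
- **That withdrawal is a way to drop poor responders.** None of the three reasons in 5.3 is poor response. With loss to follow-up, the outcome is already missing. This route is mainly a missing-data matter under 11.4.
- **That investigators who know the arm make the decision.** Section 11.5 does not say who decides. The open design permits it, and no safeguard prevents it.
- **That ITT was rejected, or that patients change arms.** The ITT/PP mark is unreadable, and nothing moves a retained patient between arms. The supportable statement is that not all randomised patients need be included.
- **That the device effect is inflated.** No rule targets poor outcomes, so the direction is unknown.

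Section 11.5 also requires recorded reasons for unused data. That makes exclusions traceable, but it does not prevent bias.

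**Conclusion.** The point holds in limited form. It rests on three readable facts: an exclusion rule without a time limit or blinding, an analysis population not defined by randomisation, and an open design. The bias is possible, not demonstrated. The illustrated shift, about 0.4 of a standard error, is modest and depends wholly on the assumed counts, outcome gap and 30 per arm; it could be nil or of opposite sign. Whichever box was marked in the synopsis, the text needs work: an ITT mark would contradict 11.3 to 11.5, and a PP mark would confirm that the primary set is not all randomised patients. This should be corrected, with medium confidence in its practical importance.

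**What to change.** 1. In 11.3 and 11.5, define the primary FMA-UE set as all randomised patients in their allocated arm, whatever is later found about eligibility, cooperation or amount of training completed.
2. Limit the 11.5 exclusion to patients not yet randomised and to the retrospective records. Report the randomised comparison without ineligible patients as a sensitivity analysis.
3. Amend 11.4 and the synopsis so that a patient is left out of the FMA-UE analysis only when the FMA-UE value itself is missing, with numbers and reasons by arm.
4. Leave the reasons in 5.3 unchanged, but state that the post-treatment assessment already scheduled in 4.3 is still sought from withdrawn patients who agree and can be assessed.
5. Make the ITT/PP field in the synopsis agree with the revised sections.

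The cost is wording, one sensitivity analysis and some follow-up effort. The downside is that a few ineligible patients stay in the primary set and may slightly dilute the effect. Patients with no FMA-UE value are still omitted, so step 4 matters. This is a cheap improvement.
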